8.2. Handling of Dropouts, Missing Data

Time to event analysis:

The Cox proportional hazards regression model analysis will be based on methods for right-censored data ([Lindsey](#), 1998).

In this setting, the event/failure will be represented by having a RVNA concentration <0.5 IU/mL (see section [8.8](#)). Subjects without event (with missing blood draw, or lost to follow up or early terminated) will be regarded as right-censored data.

GMC and percentage analysis - boostability:

To evaluate the booster response in terms of Geometric Mean Concentration (GMC), Geometric Mean Ratio (GMR) and percentage of subjects with RVNA concentration ≥ 0.5 IU/mL; missing data will be not included in the analysis.

GMC and percentages of subjects with RVNA concentrations ≥ 0.5 IU/mL

To evaluate the long-term (up to approx.10 years) immunogenicity in subjects who received a primary series of accelerated or conventional rabies PrEP in the parent study (V49_23) in terms of GMC and percentage of subjects with RVNA concentration ≥ 0.5 IU/mL; missing data as such will be not included in the analysis. If a subject receives a rabies vaccine booster dose, the RVNA value after booster will be set to half of quantification level from that moment onward. This because the exposure to a booster dose during the trial introduces a bias, as the RVNA concentrations will reflect the booster response and not the long-term persistence after the primary series (i.e., vaccination received at time of parent study).

8.2.1. Safety Data

Safety data (i.e., unsolicited serious adverse events) will be collected and analyzed only for subjects who will receive at least one booster dose during the trial.

No imputation methods will be used to address missing values.

8.2.2. Immunogenicity Data

Immune response in subjects with or without booster will exclude missing values, assuming missing immunogenicity values as Missing Completely At Random (MCAR) and therefore will not contain information that impact the result of the analysis (i.e., not informative).

Imputation methods will be used for those subjects who will receive a booster dose during the trial i.e., once the RVNA concentration fall below the predefine cut-off of 0.5 IU/mL, that value will be set up to half of quantification level from that moment onward.

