7.3. Full Analysis Set (FAS), Immunogenicity

FAS-1: Booster immunogenicity analysis

All subjects in the Enrolled Set who receive at least one booster dose during the trial (because RVNA value below 0.5 IU/mL at scheduled visit) or before entering the trial (e.g. travellers to endemic areas or veterinarians who got the booster regardless of the RVNA value) and provide immunogenicity data.

FAS-2: Long term immunogenicity analysis

All subjects in the Enrolled Set who provide immunogenicity data.

Note: In the long-term immunogenicity analysis, when a subject receives a rabies vaccine booster dose (before or during the study) because RVNA value is below 0.5 IU/mL, subsequent RVNA values after the booster dose will be set to half of the detection level (i.e. 0.1 IU/mL) until study end even if the subject withdraws earlier than last study visit (see last part of section [8.2](#) for a detailed explanation).

In case a subject receives a booster dose before or after entering the study (e.g. travellers to endemic areas, veterinarians) but the last known RVNA value was above 0.5 IU/mL, then he/she will be excluded from the long term immunogenicity analysis set (i.e. FAS-2 and PPS). This is justified by the fact that including actual values as recorded after the booster dose would inflate the immunogenicity persistence; on the other hand, it would be inappropriate to apply the same rule used for subjects receiving a booster dose when RVNA value is less than 0.5 IU/mL as this is not the case.

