All further subject immunogenicity data will not be used for Time to event analysis.

GMC and percentage analysis - boostability:

Subject is included in the Exposed to Booster Set and independently on time or visit in which booster is administered the time-points will be as following:

- Pre-booster
- 7 days after booster
- 6 to 9 months after booster

Long-term persistence of antibody responses after primary series

All immunogenicity data until booster will be part of analysis as they are reported.

For subjects receiving a booster dose, the following method of imputation will be used for antibody values:

- Values, missing or not, will be replaced with half of the quantification level (0.1 IU/mL) from that moment onward.

Subjects receiving a booster dose outside of the study and for which RVNA value at the time of booster vaccination is not available will be excluded from FAS-2 and PPS-2 (see section 7.3 for details)

Duration in the Study

Duration in the study is defined in days as:

Last visit date (visit x)^a – Enrollment date (visit 1) + 1

^a or premature discontinuation date (in case of withdrawal from the study)

The duration is missing if one of the dates is missing or incomplete.

Unsolicited Serious Adverse Events

All serious adverse events (AEs) following *Rabipur* booster dose within the study will be characterized according to the date of occurrence related to the vaccination phase as follows:

- **Emergence before vaccination phase:** start date before the first date of injection of study vaccine.
- **Emergence during vaccination phase:** start date on or after the first date of injection of study vaccine or, adverse event increase in severity including to “serious” AE.

If start date is equal to the first date of injection then “timing” variable (“On injection day, before injection”/“On injection day, after injection”) will be used to define whether the adverse event occur before or after the injection.

If an AE start date is missing or unknown, the AE will be considered as emergent.

When start and/or end dates of an AE are only partially known, AEs will be categorized as emergent before, during, or after vaccination phase using the following rules:

- If the partial end date is before ($<$) the first study vaccination (i.e., year or year & month is/are before the first study vaccination year or year & month) then the AE is emergent before vaccination phase.

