11.3. Secondary Objectives Analysis

Secondary Immunogenicity Objective:

To evaluate the long-term (up to approx.10 years) immunogenicity in subjects who received a primary series of accelerated or conventional rabies PrEP intramuscular (IM) regimen in the parent study V49_23.

Yearly Geometric Mean Concentrations up to Year 10

All subjects enrolled in this extension study, independently from booster administration, are planned to be followed until year 10 from the primary vaccination.

Log-transformed antibody titers as collected at annual Scheduled Clinic Visits (from Visit 1 to Visit 7) will be analyzed using a mixed model for repeated measures within subject, including time, center and treatment as independent variables, interaction for time and treatment, a random intercept with an unstructured covariance matrix.

SAS code will look like the following:

```
PROC MIXED DATA = model;
  class subject time treatment center;
  model log_Ab = time treatment time*treatment center/ CL s ;
  lsmeans time treatment time*treatment;
  random intercept / subject = usubjid type = UN;
RUN;
```

Reverse Cumulative Distribution Figure (RCDF) up to Year 10

The percentages of subjects with concentration greater than or equal to defined RVNA values (on log10 scale) will be presented as reverse cumulative distribution curve, having the individual RVNA concentration on the X-axis and the percentage of subject with equal to or greater than the value on the Y-axis by each study visit (i.e., Year)

Note: If subject receives a booster during the study, for the purpose of the secondary objective analysis on long-term persistence of immune responses the RVNA concentration after the booster will not be 'entered' as such, but half of quantification level from that moment will be used for all consecutive visits.

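### SAP 8.2.2, read as written, overwrites the measured pre-booster result below 0.5 IU/mL in boosted subjects, while SAP 7.3, 8.2, 8.8 and 11.3 replace only values after the booster

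*SAP*

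**What the plan says.** Five places in the SAP describe the replacement of RVNA values in boosted subjects.

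- **SAP 8.2.2 (Immunogenicity Data)** first sets the scope: "Imputation methods will be used for those subjects who will receive a booster dose during the trial". It then gives the rule: "once the RVNA concentration fall below the predefine cut-off of 0.5 IU/mL, that value will be set up to half of quantification level", from that point on. The trigger is the fall below 0.5 IU/mL, and the value replaced is the one that fell.
- **SAP 8.8 (long-term persistence)**: "All immunogenicity data until booster will be part of analysis as they are reported". For boosted subjects it adds: "Values, missing or not, will be replaced with half of the quantification level (0.1 IU/mL) from that moment onward".
- **SAP 8.2 (GMC and percentages)**: "If a subject receives a rabies vaccine booster dose, the RVNA value after booster will be set to half of quantification level from that moment".
- **SAP 7.3 (note to FAS-2)**: "subsequent RVNA values after the booster dose will be set to half of the detection level (i.e. 0.1 IU/mL) until study end".
- **SAP 11.3 (note on the secondary analysis)**, for RVNA after the booster: "half of quantification level from that moment will be used for all consecutive visits".

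In the last four the trigger is the booster, and only values after it are replaced. No text says which section prevails.

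The Protocol (Synopsis, Ad hoc Clinic Visits, and Table 2b) places the booster about 6 to 9 months after the Scheduled Clinic Visit whose result qualified the subject.

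**The concern.** The qualifying sample precedes the booster, so the two rules cannot agree on it unless the measured result happens to equal the replacement value.

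SAP 8.2 gives the reason for replacement: after a booster, the concentration reflects the booster response and not persistence after the primary series. That reason does not apply to a sample drawn months earlier, which is a valid persistence measurement. SAP 8.2.2 would discard it because of something that happens later.

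Equal results would then be scored differently. Take two subjects measured at 0.4 at Year 5. The one who is later boosted would be analysed as 0.1, and the one who is never boosted as 0.4. The documents foresee unboosted subjects below 0.5: missed Ad hoc Visits (Protocol 3.8), exclusions before the booster (Protocol 4.2), and deviation code 1070 for a booster not given (SAP Table 4). A drop first seen at Year 10 leads to no in-study booster, so it would stay as measured while the same drop at Years 3 to 9 would be overwritten.

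The outputs at stake are secondary endpoints (Protocol 8.1.2.3): the yearly GMCs and the reverse cumulative distribution curves.

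**Working it through.** The plan gives no figure to reproduce here, since SAP 5 states that no sample size or power analysis was done. The check sets the two rules side by side and works out how far they diverge.

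**Inputs from the documents**
- Replacement value: 0.1 IU/mL (SAP 7.3 and 8.8).
- Reported results below 0.5: <0.1, 0.1, 0.2, 0.3 and 0.4 (SAS code in SAP 8.8).

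**Assumed inputs (not in the documents)**
- p: the share of an arm newly below 0.5 at a visit and later boosted.
- g: the geometric mean of those subjects' measured values. An even mix of 0.1, 0.2, 0.3 and 0.4 gives g = (0.1 × 0.2 × 0.3 × 0.4)^(1/4) = 0.22. I also use g = 0.3.

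**One subject.** Setting a measured 0.2, 0.3 or 0.4 to 0.1 moves log10 RVNA by −0.301, −0.477 or −0.602. A measured 0.1 does not move.

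**Visit GMC.** The arm's mean log10 value changes by p × log10(0.1/g), so

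GMC under 8.2.2 ÷ GMC under 8.8 = (0.1/g)^p

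| p | g = 0.22 | g = 0.3 |
|---|---|---|
| 5% | 0.96 | 0.95 |
| 10% | 0.92 | 0.90 |
| 25% | 0.82 | 0.76 |

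For p = 25%, g from 0.2 to 0.4 gives 0.84 to 0.71.

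**Ratio between arms.** With p = 25% in one arm, 10% in the other and the same g in both, the GMC ratio is multiplied by (0.1/g)^(0.25 − 0.10). That is 0.89 for g = 0.22 and 0.85 for g = 0.3.

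**Reverse cumulative distribution.** Take p = 20%, spread evenly over 0.1 to 0.4, with everyone else at or above 0.5:

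| Threshold (IU/mL) | % at or above, 8.8 | % at or above, 8.2.2 |
|---|---|---|
| 0.2 | 95 | 80 |
| 0.3 | 90 | 80 |
| 0.4 | 85 | 80 |
| 0.5 | 80 | 80 |

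**What does not change.** The measured and the replaced value are both below 0.5, so the percentage at or above 0.5 is the same. So is time to event, which SAP 8.8 dates to the visit at which the drop is observed.

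**Limits of the arithmetic.** The formula is for raw means. SAP 11.3 plans a mixed model with centre and a random intercept, so its estimates will not match exactly. The replacement value is also unsettled: 0.1 as half the quantification level implies a limit of 0.2, yet the code lists <0.1 and 0.1 as results. With a replacement value of 0.05, the factor for g = 0.3 and p = 20% is 0.70 instead of 0.80.

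**The case against.** The strongest reply is that 8.2.2 is shorthand and not a rival rule. Elsewhere the SAP uses the drop and the booster interchangeably: SAP 8.1 equates the first booster with RVNA below 0.5, and SAP 8.8 glosses receipt of a booster the same way. Four sections agree against one. Two of the four are the most specific: the 8.8 text under the heading for this analysis, and the 11.3 note in the section that defines the GMCs and curves. Applied literally to all immunogenicity data, 8.2.2 would also wipe out the 7-day post-booster results, which cannot be intended. A careful programmer would most likely follow 8.8.

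Most of this stands. 8.2.2 is the outlier, and the SAP does not offer two equally supported definitions. But its sentence is current text, it yields a different data set, and nothing ranks the sections.

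Three stronger readings are tempting, and the documents support none of them.

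- **That the rule exaggerates the difference between regimens.** This needs the arm with the lower GMC to have more new, measurable drops at the visit. SAP 11.2 mentions a difference in persistence at Day 366 of the parent study, but gives neither its size nor the drops by visit in the extension.
- **That the effect is greatest at Year 3.** Every in-study drop at Year 3 is new, but the number and level of new drops at later visits are unknown.
- **That the primary booster GMR is affected.** Using 0.1 as the denominator would raise a subject's ratio 2-, 3- or 4-fold for a measured 0.2, 0.3 or 0.4. But SAP 11.2 takes the baseline as detected at the previous Scheduled Visit, which rules that use out.

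**Conclusion.** The inconsistency is real and narrow. As written, SAP 8.2.2 replaces a valid pre-booster measurement that SAP 8.8 requires to be kept, and 7.3, 8.2 and 11.3 side with 8.8. It reaches only subjects boosted in the trial, at drop visits in Years 3 to 9. Usually that is one visit per subject; it can be more if an Ad hoc Visit is missed and the booster comes a cycle later.

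The size cannot be fixed from the documents. Under the assumed values of p and g, a visit GMC would fall by roughly 4% to 24%, and a between-arm GMC ratio would shift by about 11% to 15% when new drops are 25% against 10%. The direction of any effect on the regimen comparison depends on which arm has more new drops.

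The affected outputs are secondary and carry no hypotheses (Protocol 8.4.3.3.1). The point is worth correcting because the outcome otherwise depends on which section is programmed.

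**What to change.** Reword the sentence in SAP 8.2.2 to match 8.8:

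- All values up to and including the last draw before the booster are analysed as measured, with results below LQ set to LQ/2.
- Replacement applies only in the long-term persistence analysis, and only to draws after the booster date.

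The programming specification should use the booster date as the trigger, not the date of the drop. The same edit can state the quantification limit, so that its half is unambiguous.

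The cost is one sentence, with no new data and no change to study conduct. The documents do not say which rule the Year 6 interim programs used, so that should be checked before interim and final GMCs are compared.

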8.3. Multicenter Studies

Long-term persistence of antibody responses after primary series

Both time-to-event and persistence analyses will include term for center.

Boostability analysis

Geometric mean concentration analysis will be estimated using a two-way ANOVA including treatment and center.

If the statistical model does not converge due to the factor “center”, a model without center effect will be fitted instead.

8.4. Multiple Comparisons and Multiplicity

No adjustment was made due to multiplicity.

8.5. Immunogenicity Subsets

Descriptive statistics of RVNA persistence following a booster dose administration will be carried out at the end of the study. This will include subjects in the FAS-1 aggregated by year of booster receipt: i.e. subset FAS-1 year 3, FAS-1 year 4 and so forth.

8.6. Subgroups

Not Applicable.

No subgroup analysis will be performed but a contingency table analysis will be created counting the frequency of subjects who receive 0 booster dose, 1, 2, 3 or more booster doses.

8.7. Data Transformation

Distributions of antibodies are generally skewed to the right (Nauta, 2010). Therefore, antibody concentrations will be log10-transformed. GMCs and their 95% Confidence Intervals (CIs) are computed by exponentiating (base 10) the least squares means and 95% CIs of the log10 concentrations.

8.8. Derived and Computed Variables

Data from parent study (V49_23)

Time to event analysis

For time to event analysis (i.e., Kaplan-Meier (KM) and Cox proportional hazard regression model), immunogenicity data from parent study, from day 57 up to one year, as well as data related to time between the end of parent study and start of this study (i.e., if subject receives a booster between the two studies) will be considered, as estimation of time to RVNA concentration drop below 0.5IU/mL.

Long term immunogenicity analysis

Demographics

Race and Age at time of V49_23 enrolment will be derived from demography of the parent study.

Body Mass Index (kg/m²) (BMI) will be calculated using the following formula: Weight (kg) / Height² (m²)

Time to Event

Survtime represents time to event/censoring in years:

Survtime variable will be derived using the planned visit day at which the event occurred or the subject is censored as time point.

The following SAS code describes how to derive **Survtime** from V49_23 study and from the current study (V49_23E1).

```

DATA <dbname>;
  SET <dbname>;
  IF LBORRES IN ('<0.1', '0.1', '0.2', '0.3', '0.4')
  THEN DROP ='Y';
  ELSE DROP ='N';
  format LABEL $12.;
  IF STUDYID = 'V49_23' THEN DO;
    IF VISITNUM = 9 THEN do;POINT =1; YEAR =57; LABEL = 'Day 57'; end;
    IF VISITNUM = 10 THEN do;POINT =2; YEAR =91; LABEL = 'Day 91'; end;
    IF VISITNUM = 11 THEN do;POINT =3; YEAR =181; LABEL = 'Day
181';end;
    IF VISITNUM = 12 THEN do;POINT =4; YEAR =365;LABEL = 'Day 366';end;
  END;
  IF STUDYID = 'V49_23E1' THEN DO;
    IF VISITNUM = 1 THEN do; YEAR = 3*365; LABEL = 'Year 3'; end;
    IF VISITNUM = 2 THEN do; YEAR = 4*365; LABEL = 'Year 4'; end;
    IF VISITNUM = 3 THEN do; YEAR = 5*365; LABEL = 'Year 5'; end;
    IF VISITNUM = 4 THEN do; YEAR = 6*365; LABEL = 'Year 6'; end;
    IF VISITNUM = 5 THEN do; YEAR = 7*365; LABEL = 'Year 7'; end;
    IF VISITNUM = 6 THEN do; YEAR = 8*365; LABEL = 'Year 8'; end;
    IF VISITNUM = 7 THEN do; YEAR = 9*365; LABEL = 'Year 9'; end;
    IF VISITNUM = 8 THEN do; YEAR = 10*365; LABEL = 'Year 10';end;
  END;
  Survtime= YEAR;

  IF DROP ='Y' THEN CENSOR=1; ELSE CENSOR = 0;
RUN;

```

Censor: represents censoring indicator variable: 0=censored, 1=event of interest;

Event of interest: RVNA concentration < 0.5 (censor=1)

If one of the followings occur, subject will be censored (censor=0) and time to the last data available strictly before the event will be included in the survival analysis:

- Subject is lost to follow up
- Subject withdraws consent
- RVNA concentration not available for last visit (last visit could differ from the final visit)
- Subject receives booster (study vaccine or another rabies vaccine) but RVNA concentration ≥ 0.5 or unknown
- Subject performs final visit (i.e., study termination visit) and RVNA concentration is ≥ 0.5 IU/mL (for the purpose of the IA, if visit 4 is completed by the subject he will be considered as a censored value at the time of visit 4)

The subjects will be considered as censored if any of the following event occurs before the subject's antibody titer level goes beyond the level of 0.5IU/mL:

- All further blood draw results are missing

Censor variable will be set to 0 if any of the case above occurs. If the subject's antibody level titer goes beyond 0.5 IU/mL censoring values will be set to 0 at the time of the 1st antibody titer level below 0.5 IU/mL.

Point Variable describes the order of RVNA concentration observed. It will be POINT=5 if a subject receives booster between V49_23 END (last visit date) and V49_23E1 START (first visit date).

Immunogenicity

Values below the limit of quantification (recorded as “< LQ”) will be set to half that limit (i.e., LQ/2]).

Geometric Mean Concentration

The GMC will be calculated using the following formula:

$$10^{\left[\frac{\sum_{i=1}^n \log_{10}(t_i)}{n} \right]}$$

where t_1, t_2, \dots, t_n are n observed immunogenicity titers/concentrations.

Geometric Mean Ratio

Geometric mean ratios (GMRs) measure the changes in immunogenicity concentrations *within* subjects.

The GMR will be calculated using the following formula:

$$10^{\left[\frac{\sum_{i=1}^n \log_{10}\left(\frac{v_{ij}}{v_{ik}}\right)}{n} \right]} = 10^{\left[\frac{\sum_{i=1}^n \log_{10}(v_{ij}) - \log_{10}(v_{ik})}{n} \right]}$$

where, for n subjects, v_{ij} and v_{ik} are observed immunogenicity titers/concentrations for subject i at time-points j and k , $j \neq k$.

Imputation of RVNA concentration in subjects receiving a booster

Once a subject receives a rabies vaccine booster dose (i.e. RVNA<0.5) he/she will be treated as follows:

Time to event analysis:

Censor=1 for the time-point in which RVNA is observed being below 0.5 IU/mL

All further subject immunogenicity data will not be used for Time to event analysis.

GMC and percentage analysis - boostability:

Subject is included in the Exposed to Booster Set and independently on time or visit in which booster is administered the time-points will be as following:

- Pre-booster
- 7 days after booster
- 6 to 9 months after booster

Long-term persistence of antibody responses after primary series

All immunogenicity data until booster will be part of analysis as they are reported.

For subjects receiving a booster dose, the following method of imputation will be used for antibody values:

- Values, missing or not, will be replaced with half of the quantification level (0.1 IU/mL) from that moment onward.

Subjects receiving a booster dose outside of the study and for which RVNA value at the time of booster vaccination is not available will be excluded from FAS-2 and PPS-2 (see section 7.3 for details)

Duration in the Study

Duration in the study is defined in days as:

Last visit date (visit x)^a – Enrollment date (visit 1) + 1

^a or premature discontinuation date (in case of withdrawal from the study)

The duration is missing if one of the dates is missing or incomplete.

Unsolicited Serious Adverse Events

All serious adverse events (AEs) following *Rabipur* booster dose within the study will be characterized according to the date of occurrence related to the vaccination phase as follows:

- **Emergence before vaccination phase:** start date before the first date of injection of study vaccine.
- **Emergence during vaccination phase:** start date on or after the first date of injection of study vaccine or, adverse event increase in severity including to “serious” AE.

If start date is equal to the first date of injection then “timing” variable (“On injection day, before injection”/“On injection day, after injection”) will be used to define whether the adverse event occur before or after the injection.

If an AE start date is missing or unknown, the AE will be considered as emergent.

When start and/or end dates of an AE are only partially known, AEs will be categorized as emergent before, during, or after vaccination phase using the following rules:

- If the partial end date is before ($<$) the first study vaccination (i.e., year or year & month is/are before the first study vaccination year or year & month) then the AE is emergent before vaccination phase.
- If the partial start date is equal or after (\geq) the first study vaccination (i.e., year or year & month is/are after or the same as the first study injection year or year & month) then the AE is emergent during vaccination phase.

The **maximum event severity** is the greatest severity associated with a preferred term (PT) for a reported AE according to the following order: Mild < Moderate < Severe. Unknown/ Missing severity is considered as severe (except for the definition of emergence).

Multiple AEs with the same PT for the same subject are counted only once.

Vaccination-related AEs are those for which the cause has been evaluated by the investigator, and recorded either as possibly related, probably related or unknown/ missing.

Pre-study, Concomitant and Post-Vaccination Medications

A **prior medication** is a medication received by the subject prior to the start of V49_23E1 (i.e. Termination visit date for V49_23 \leq medication start date $<$ start of this extension study V49_23E1).

A **concomitant medication** will include drugs (antipyretics and/or analgesic medications within 24 hours prior to vaccination) and all medications (including vaccines) from the time of the boost per administration until the day of next Scheduled Clinic Visit. (i.e. medication start date \geq booster administration date).

Concomitant medications, as defined in study protocol, include all medications (including vaccines) taken by/administered to subjects who experienced Serious Adverse Events (SAEs) during the safety follow up period (which is, the day of the next Scheduled Clinic Visit after booster vaccination or the date of Early Termination Visit, whichever is earlier) after administration of the rabies vaccine booster dose. In case of start date of a medication intake is missing, the medication is considered as concomitant.

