11.2. Primary Objectives Analysis

Primary Immunogenicity Objectives:

1. To compare the long-term (up to approx.10 years) persistence of antibody responses (i.e. time until antibody concentrations drop below 0.5 IU/mL) in subjects who received a primary series of accelerated or conventional rabies PrEP intramuscular (IM) regimen in the parent study V49_23.
2. To evaluate the antibody responses to a booster dose of Purified Chick Embryo Cell-Culture (PCEC) rabies vaccine administered to subjects with Rabies Virus Neutralizing Antibody (RVNA) concentrations < 0.5 IU/mL following a primary series of accelerated or conventional rabies PrEP IM regimen in the parent study V49_23.

Primary hypotheses:

There is no null hypothesis associated to primary objectives.

Time to first RVNA concentrations < 0.5 IU/mL

Cox proportional hazards regression model

Since, already at the end of the parent study (Day 366, study V49_23) it was observed a difference in the persistence of adequate RVNA concentrations between subjects who have received the accelerated PrEP schedule and those who received the conventional rabies vaccines schedule, the HR from the Cox proportional hazards regression model will be used as a treatment effect measure for time to event endpoints.

Statistical model:

An adjusted proportional hazards regression Cox model will be used:

$$h(t) = h_0(t) \cdot \exp(\beta_1 x_1 + \beta_2 x_2)$$

where:

t represents the survival time

$h(t)$ is the hazard function as determined by the covariates treatment and center

$h_0(t)$ is the baseline hazard function at time t

X_1 represents treatment

X_2 represents center

β_1 and β_2 are the unknown parameters for treatment and center, to be estimated.

The HR is a multiplicative constant $\exp(\beta_1)$ comparing the hazard function in the accelerated schedule group relative to the hazard function in the conventional schedule group.

The HR will be derived from the Cox proportional hazards model using SAS PROC PHREG (with TIES=EXACT).

HR point estimate(s) will be based on partial maximum likelihood function, and Wald-test based two-sided 95% confidence intervals will be requested by the RISKLIMITS option.

The following SAS code will be applied:

```
PROC PHREG data=<dataset>;
  class arm center;
  MODEL survtime*status(0)=ARM center/ TIES=EXACT RISKLIMITS;
  RUN;
```

survtime represents variable containing event/censoring times.

status represents censoring variable (0=censored, 1=event).

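### SAP 8.8 flags the primary event by matching five text strings, and this is not reconciled with the SAP's own assay limit, censoring time, row selection and indicator coding

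*SAP*

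**What the plan says.** SAP 8.8 defines the event in words as "Event of interest: RVNA concentration < 0.5 (censor=1". The code flags it with "IF LBORRES IN ('<0.1', '0.1', '0.2', '0.3', '0.4". A record that matches one of these strings gets DROP='Y' and any other record gets 'N', after which "IF DROP ='Y' THEN CENSOR=1; ELSE CENSOR = 0" applies. On timing, "Survtime variable will be derived using the planned visit day at which the event occurred or the subject is censored as time point".

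Three other rules in the SAP bear on this code.

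- **Assay limit.** SAP 8.8 replaces results recorded as below the limit of quantification by half that limit. For boosted subjects, values "will be replaced with half of the quantification level (0.1 IU/mL) from that moment onward". SAP 7.3 says "subsequent RVNA values after the booster dose will be set to half of the detection level (i.e. 0.1 IU/mL", calling the limit a detection level. Neither document gives the limit outright as a number, or the number of decimals reported.
- **Censoring.** For subjects without an event, SAP 8.8 says "time to the last data available strictly before the event will be included in the survival analysis". It also says that data after the event are not used in the time-to-event analysis.
- **Models.** SAP 11.2 fits the Cox model with "MODEL survtime*status(0)=ARM center/ TIES=EXACT RISKLIMITS", and the Kaplan-Meier code there also reads `status`.

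**The concern.** This code defines the event for the first primary objective, so the Kaplan-Meier curves and the hazard ratio depend on it. An exact text match is correct only if the laboratory reports results in precisely the listed forms. The SAP's own statement about half the limit suggests that the lowest results may be reported in a form that is not listed.

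A subject whose first low result is missed would still be boosted, because Protocol 3.1 bases that decision on a sponsor listing of individual titres. After the booster, later results would probably be at or above 0.5, so the code might never recover the event. The curve would then overstate persistence. Separately, blank records and repeated rows can inflate time at risk whatever the assay limit is.

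**Working it through.** **1. The limit (SAP 7.3 and 8.8).** The rule is imputed value = LQ/2.

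- If 0.1 is the half, LQ = 2 × 0.1 = 0.2. The stated imputation value is reproduced. Results below the limit would read `<0.2`, which is not listed, while the listed `<0.1` and `0.1` could not occur.
- If `<0.1` in the code shows the limit, LQ = 0.1 and LQ/2 = 0.05. The stated 0.1 is then twice what the rule gives, unless the bracket names the limit itself. Both 0.05 and 0.1 lie below 0.5, so this touches only the secondary GMC analysis and not the primary event.

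**2. The text match.** I applied the five-string test, ignoring trailing blanks, to 13 strings that all denote results below 0.5.

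- Flagged (5): `<0.1`, `0.1`, `0.2`, `0.3`, `0.4`.
- Not flagged (8): `<0.2`, `< 0.1`, `<0.10`, `0.15`, `0.25`, `0.40`, `0.45`, `0.49`.
- A blank also returns CENSOR=0.

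A numeric test (below 0.5, with any below-limit result counted as an event) flags all 13.

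**3. Effect on a curve (illustration).** Take ten subjects, four truly below 0.5 at Year 3, two of them reported as `<0.2`.

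- Numeric rule: S(3) = 1 − 4/10 = 0.60.
- SAP code: S(3) = 1 − 2/10 = 0.80.

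**4. Share of first events missed.** The inputs are assumptions, because the documents give none: Year 3 median 1 or 2 IU/mL, log10 SD 0.4 or 0.6, decline 0.05 log10 per year, assay SD 0.12 log10, eight annual draws, results truncated to the reported decimals.

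| Median, SD | LQ 0.1, one decimal | LQ 0.2, one decimal | LQ 0.1, two decimals | LQ 0.2, two decimals |
|---|---|---|---|---|
| 1, 0.4 | 0% | 7.5% | 98.7% | 100% |
| 1, 0.6 | 0% | 21.5% | 91.3% | 100% |
| 2, 0.4 | 0% | 2.9% | 99.8% | 100% |
| 2, 0.6 | 0% | 14.0% | 95.5% | 100% |

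With LQ 0.2 and one decimal, the missed events are all the lowest values.

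**5. Blank records.** Suppose a subject's last result is at Year 3 and blank records run to Year 10. The text censors at Year 3. The code produces a CENSOR=0 record at Year 10.

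**6. Row selection.** The code makes one row per visit and has no step that keeps the first event or the last available draw. Take 100 subjects with all 12 planned draws (four from the parent study, eight annual). Ten are below 0.5 at Year 3 only, and every other result is at or above 0.5.

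- One row per subject: S(Year 3) = 1 − 10/100 = 0.90.
- Stacked rows: Years 3 to 10 give 8 × 100 = 800 rows at risk, so S(Year 3) = 1 − 10/800 = 0.9875.

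This assumes that the indicator has been renamed. As printed, the code creates `CENSOR` while both procedures read `status`.

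**7. The indicator in the text.** One sentence in SAP 8.8 sets censoring to 0 at the first titre below 0.5. The code, the event definition just after it, and the later imputation paragraph of the same section all give that time-point the value 1.

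**The case against.** The best defence is that the list itself indicates the reporting format: a limit of 0.1 and one decimal. Under that format it captures every result below 0.5. The string `<0.2` appears nowhere in either document, and the bracketed 0.1 in SAP 8.8 can be read as naming the limit. This stands. A reader might infer that the list cannot agree with the quantification limit, but the documents support only an unresolved conflict. SAP 7.3 leans towards 0.2, because its bracket follows the phrase about half the level.

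The code is also introduced as showing how to derive the survival time, so a final step that reduces the data to one row per subject may simply not be printed. The variable `status` is defined with the same coding as `CENSOR`. The text of SAP 8.8 makes a boosted low-titre subject an event and bars later data. A reader might infer that the plan intends such subjects to stay event-free to Year 10; the text says otherwise. What remains is that the printed code does not carry out the text, and that the text contradicts itself on the indicator.

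Two further inferences go too far.

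- **Missing as waned.** A missing result is not evidence of waning, and censoring such subjects is the SAP's stated rule. Only the time is wrong, and only if blank records exist in the dataset, which the documents do not say.
- **Biased arm comparison.** SAP 11.2 reports a persistence difference between schedules by Day 366, so unequal loss of low values is possible. Its effect on the hazard ratio was not calculated, and nothing in the documents settles it.

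**Conclusion.** Wrong as written. The primary event derivation is not reconciled with the SAP's own rules on the assay limit, the censoring time, the use of data after the event, and the value of the indicator.

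The size depends on two facts that the documents do not state. With a limit of 0.1 and one decimal, no first events are missed and only the post-booster imputation value is in question (0.1 against 0.05). With a limit of 0.2 and one decimal, 3–22% are missed. With two decimals, 91–100% are missed. All three figures rest on the assumed distributions above.

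The faults in row selection, indicator name and the reversed sentence do not depend on the limit. Booster allocation is unaffected, because it uses the titre listing and not this code.

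**What to change.** In SAP 7.3 and 8.8:

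- State one numeric assay limit under one name, and make the post-booster imputation value equal to half of it.
- Define the event numerically: result below 0.5 IU/mL, or reported as below the limit.
- Leave missing results as missing.
- Keep one row per subject: the first event, otherwise the last available draw.
- Use one indicator name in the derivation, the Cox code and the Kaplan-Meier code.
- Correct the sentence that sets censoring to 0 at the first titre below 0.5.

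The cost is a few lines of code and SAP text, with no new data.
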